10.0 Efficacy Analysis

10.1 General Considerations

The treatment effect will be evaluated based on a two-sided significance level of 0.05 (when rounded to three decimal places).

The Primary Analysis for Period B re-randomized subjects will be conducted after the last patient either has completed Week 52 visit or discontinues from the study, and at the time approximate to the database lock of all other global pivotal Phase 3 psoriasis studies, whichever occurs later. All endpoints will be analyzed up to Week 52, with the following exception:

- Categorical endpoints related to PASI and sPGA, using the LOCF method (defined in Section 10.1.4), will be analyzed up to the last visit that at least one subject has observed PASI and sPGA measurements, respectively.

To best maintain the study integrity for data beyond Week 52, blinded treatment assignments will not be disseminated to the sites, investigators, and patients until the end of study database lock.

Efficacy variables will be summarized in all efficacy populations. The efficacy analysis will be conducted in the ITT_A1 and the ITT_B_R populations. Only the primary and ranked secondary variables will be analyzed for the per-protocol populations using primary approach to handle missing data as described below.

Subjects' actual weight category and prior TNF antagonist exposure will be used as the strata in the stratified analyses.

10.1.1 **Analyses of Categorical Variables**

For categorical variables, frequencies and percentages will be summarized. Treatment comparison will be conducted using a Cochran-Mantel-Haenszel (CMH) test with stratification factors as strata for the analysis. The CMH test will use weights proposed by Greenland & Robins, which is calculated as follows:

$$\hat{\delta}_{MH} = \frac{\sum_{i=1}^u w_i \cdot \hat{\delta}_i}{\sum_{i=1}^u w_i}, \text{ where}$$

$\hat{\delta}_i = \frac{x_i}{n_i} - \frac{y_i}{m_i}$ denotes the risk difference in stratum $i, i = 1, \dots, u$

$w_i = \frac{n_i \cdot m_i}{n_i + m_i}$ denotes the weight of stratum $i, i = 1, \dots, u$

x_i denotes the number of patients with event in treatment₁ in stratum $i, i = 1, \dots, u$

y_i denotes the number of patients with event in treatment₂ in stratum $i, i = 1, \dots, u$

n_i denotes the number of patients on treatment₁ in stratum $i, i = 1, \dots, u$

m_i denotes the number of patients on treatment₂ in stratum $i, i = 1, \dots, u$

The estimated variance of $\hat{\delta}_{MH}$ is calculated as:

$$\widehat{var}(\hat{\delta}_{MH}) = \frac{\sum_{i=1}^u L_i}{(\sum_{i=1}^u w_i)^2}$$

$$\text{where } L_i = \frac{x_i(n_i - x_i) m_i^3 + y_i(m_i - y_i) n_i^3}{n_i \cdot m_i \cdot (n_i + m_i)^2}, i = 1, \dots, u$$

Assuming a normal distribution of $\hat{\delta}_{MH}$, an approximate 95% CI is given as follows, where $z_{0.975}$ is the 97.5% quantile of the standard normal distribution:

$$CI = \left[\hat{\delta}_{MH} \pm z_{0.975} \cdot \sqrt{\widehat{var}(\hat{\delta}_{MH})} \right]$$

Also, the approximate p-value can be calculated using the following:

$$\text{pvalue} = 2 \cdot \Pr \left[Z > \left| \frac{\hat{\delta}_{MH}}{\sqrt{\widehat{var}(\hat{\delta}_{MH})}} \right| \right], \text{ where } Z \sim N(0, 1)$$

If there is a stratum for a treatment group that has 0 subjects in any cell in the contingency table, all cells from the stratum will be added by 0.1 in order to prevent dividing by 0 in the above equations, as suggested in Greenland & Robins.

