7.4 INTERIM ANALYSES

There will not be an interim analysis from a statistical standpoint. An analysis will be conducted after the last patient either has been in the study for 52 weeks or discontinues from the study. All primary and key secondary endpoints are collected by Week 52; hence no alpha adjustment is required at this analysis. For this analysis all efficacy endpoints and safety will be analysed. The Sponsor will be unblinded to perform this analysis. Blinded treatment assignments will not be disseminated to the sites, investigators, and patients until the end of study database lock. If needed, more details about this analysis will be specified in the TSAP.

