7.7 DETERMINATION OF SAMPLE SIZE

This study is designed to show a difference between BI 655066 and placebo in terms of PASI90 response and sPGA scores of clear or almost clear at Week 16. However, this study was also powered to show a difference in sPGA response at Week 52 between the patients randomized to continue on BI 655066 vs. patients randomized to placebo at Week 28.

Based on the interim results from 1311.2 ([c03272682-01](#)), it is assumed at most 10% of the patients in the re-randomized BI 655066 arm will lose sPGA response of clear or almost clear (0 or 1) at Week 52 whereas approximately 25% of patients in the re-randomized placebo arm will lose response. Using a 1:2 re-randomisation scheme (BI 655066:placebo), 102 patients in the BI 655066 arm and 204 patients in the placebo arm will provide at least 90% power to detect the difference in sPGA response rate at Week 52. Assuming that 80% of patients on BI 655066 at baseline will achieve sPGA of clear or almost clear at Week 28, the total sample size required for the initial BI 655066 arm at Visit 2 is $(102)(3) \div 0.8 = 383$. See [Table 7.7:1](#) for more sample size calculations to have at least 90% power.

Table 7.7:1 Sample sizes for randomized withdrawal comparison

Response Rate at Week 52			Randomisation ratio at Week 28 active:placebo = Total N	Total N at randomisation
Active	Placebo	Delta	1:2	
90%	72.5%	17.5%	79:158 = 237	297
90%	75%	15%	102:204 = 306	383
90%	77.5%	12.5%	138:276 = 414	518

Calculated using ADDPLAN Version 6.0.4.

Thus 400 patients in the original BI 655066 arm, provide at least 90% power for the randomized withdrawal comparison. Using a 4:1 randomisation will yield a total sample size of 500 = 400:100 for BI 655066: placebo.

Based on the outcome from trials 1311.1 and 1311.2, the PASI90 response rate at Week 16 is assumed to be at least 65% in the BI 655066 arm and approximately 5% for placebo. For sPGA clear or almost clear at Week 16, the response rate for the BI 655066 arm is assumed to be at least 80% and approximately 5% for placebo. This trial will have >99% power for comparing each BI 655066 arm to placebo on both of these endpoints.

All calculations were performed using ADDPLAN Version 6.0.4, an Aptiv Solutions Company.

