4.0 Study Objectives, Design and Procedures

4.1 Primary Study Objective

The primary objective of the initial randomized phase of the study (Part A1; see Section 4.2) is to assess the efficacy of risankizumab 150 mg in comparison to placebo in subjects with moderate to severe chronic plaque psoriasis. The primary objective of the second randomized phase of the study (Part B; see Section 4.2) is to evaluate the maintenance of response with continuous risankizumab treatment compared with withdrawal of treatment.

The primary efficacy evaluation will be performed at 16 weeks. The maintenance of response following drug withdrawal will be assessed after Week 28 through the end of the study (primary evaluation at Week 52). Subsequent to drug withdrawal, subjects who experience relapse will be retreated with risankizumab to assess response after retreatment.

Evaluations of risankizumab efficacy and safety in various populations will be performed in the study to provide a full picture of risankizumab benefits and risks. These populations and the intent of the related analyses is specific in Section 5.2.

In addition, this trial will assess pharmacokinetics (PK) and the emergence of anti-drug antibodies (ADA) and their effect on efficacy and safety. Moreover, it will be explored how the use of risankizumab may influence gene and protein expression levels and disease specific protein markers. PK and ADA analyses, as well as DNA banking, exploratory biomarker, and metabolic risk factor analyses, will not be included in this SAP.

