5.0 Analysis Populations

5.1 Definition for Analysis Populations

Efficacy Population:

Intent-to-Treat (ITT) Population: The ITT Populations will be used for the efficacy analyses in different parts.

- The ITT Population in Part A1 (ITT_A1) is defined as all subjects who are randomized at Baseline. This Population will be analyzed for the efficacy of initial treatment.
- The ITT Population in Part A2 from Arm 1 (ITT_A2) is defined as all subjects who were randomized to Arm 1 at Baseline. Data from Part A2 will be used to evaluate the mid-term efficacy.
- The ITT Population across Part A2 and B from Arm 2 (ITT_ARM2) is defined as all subjects who were randomized to Arm 2 at Baseline and received at least one dose of study drug on or after Week 16. This Population will be analyzed for short and long term efficacy without initial loading dose.
- The ITT Population in Part B for re-randomized subjects (ITT_B_R) is defined as all subjects who were randomized to Arm 1 and re-randomized at Week 28. The ITT_B_R Population will mainly be used to compare efficacy of continued treatment with risankizumab vs withdrawal from the treatment. The risankizumab arm will also be summarized (including data after retreatment) for long-term efficacy with the option of re-load.
- The ITT Population in Part B for Arm 1 non-responders at Week 28 (ITT_B_NR) is defined as all subjects who were randomized to Arm 1 at Baseline, were non-responders (sPGA ≥ 2) at Week 28, and receive at least one dose of risankizumab on or after Week 28. This population will be summarized for potential delayed response.
- The ITT Population for Part B placebo patients who received retreatment (ITT_B_PBO_RT) is defined as all subjects who were re-randomized to placebo and received at least one dose of retreatment with open label risankizumab after relapse, and have the opportunity to have retreatment Week 16 assessments.

- The ITT Population for Part B risankizumab patients who receive retreatment (ITT_B_RZB_RT) is defined as all subjects who were re-randomized to risankizumab and received at least one dose of retreatment with open label risankizumab after relapse, and have the opportunity to have retreatment Week 16 assessment. The population will be summarized to examine the efficacy of re-treatment with loading dose upon relapse on risankizumab.

ITT Populations will be analyzed by the treatment group as randomized.

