10.1.4 Missing Data Imputations

Missing data will be imputed using the following methods for the efficacy analyses:

- Non-Responder Imputation (NRI): the NRI analysis will categorize any subject who does not have evaluation during a specific visit window as a non-responder for that visit. The only exception is when the subject is a responder both before and after a specific visit window, then the subject will be categorized as a responder for the visit. Only observations within the same analysis period will be used except for summary of ITT_A2 from ARM 1, where subjects' observation from Part A1 can be used since the treatment is the

same. The NRI will be the primary approach in the analyses of categorical variables.

- Last Observation Carried Forward (LOCF): The LOCF analyses will use the last observed non-missing evaluation (last completed non-missing evaluation, from composite endpoint) from the previous visit within the particular period for efficacy measures assessed to impute missing data at later visits in the same period. Baseline efficacy evaluations will not be carried forward. Of note, post-baseline observations from Part A1 can be carried forward to ITT_A2 subjects from ARM 1 since treatment is the same. LOCF will be the primary approach in the analyses of continuous variables, and the secondary approach in the analysis of categorical variables.
- As-Observed Cases (OC): The as-observed analysis will not impute values for missing evaluations, and thus a subject who does not have an evaluation on a scheduled visit will be excluded from the as-observed analysis for that visit. As-observed analysis will be the secondary approach in the analysis of continuous variables.
- Multiple Imputation (MI): The MI will be used as sensitivity approach to impute missing data in primary and ranked secondary endpoints. The variables to be included in the imputation model are listed below. If MI is not applicable due to the nature of our data (e.g., MCMC algorithm does not converge), logistic regression or mixed effect model repeat measurement (MMRM) methods will be applied as sensitivity approach, whichever applicable.

The Multiple Imputation analysis will be carried out in three steps.

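### At the Part B primary lock, LOCF fills PASI/sPGA visits after Week 52 that are not yet due, so later response rates are too high if response is still being lost

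*SAP*

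**What the plan says.** SAP 10.1 places the Part B primary analysis after the last patient has completed Week 52 or discontinued, or near the lock of the other pivotal psoriasis studies if that is later. The rule for this lock is: "All endpoints will be analyzed up to Week 52, with the following exception". The exception is categorical PASI and sPGA endpoints by LOCF, which "will be analyzed up to the last visit that at least one subject has observed PASI and sPGA measurements".

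SAP 10.1.4 defines LOCF as using the last non-missing evaluation "to impute missing data at later visits in the same period". It gives LOCF as "the secondary approach in the analysis of categorical variables"; NRI is primary. The re-randomised population ITT_B_R (SAP 5.1) "is defined as all subjects who were randomized to Arm 1 and re-randomized at Week 28", with no condition on how far a subject has been followed.

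The dated cutoffs in SAP 9.0 (01 and 22 September 2017) are for exposure only. The SAP gives no efficacy cutoff.

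**The concern.** Ordinary LOCF fills visits that a subject missed. Here, with staggered entry, it also fills visits that have not happened. A subject who is a responder at Week 52 and has simply not reached Week 76 counts as a Week 76 responder. Nothing in 10.1 or 10.1.4 excludes that subject or requires the number actually observed to be shown.

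SAP 4.1 states that "maintenance of response following drug withdrawal will be assessed after Week 28 through the end of the study", and this lock gives the first visit-wise rates past Week 52. If response continues to fall, those rates make it look more durable than the follow-up supports, and increasingly so at the later visits where durability is read.

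**Working it through.** **The plan's own figure.** Protocol 7.7 assumes that at most 10% lose response on continued drug by Week 52, and that "approximately 25% of patients in the re-randomized placebo arm will lose response". With response 0.90 vs 0.75, 1:2 allocation, two-sided 0.05, 90% power and pooled proportion (0.90 + 2×0.75)/3 = 0.80:

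n = [1.960·√(0.80·0.20·1.5) + 1.282·√(0.90·0.10 + 0.75·0.25/2)]² / 0.15² = 101.3, rounded up to 102.

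This gives 102:204, and 306/0.8 = 382.5, rounded up to 383. The stated figures reproduce, and the LOCF exception does not touch them.

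**Assumptions for the illustration (sPGA 0/1).** The documents give neither accrual nor loss after Week 52.

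- Loss continues at the Week 28-52 rate and is permanent: withdrawal S(w) = 0.75^((w−28)/24), continued S(w) = 0.90^((w−28)/24).
- Follow-up at the lock is evenly spread over Weeks 52-82 and unrelated to response. One fifth of subjects then have each of Weeks 52, 58, 64, 70 and 76 as their last visit (SAP Table 8 schedule).
- LOCF rate at week W = mean of S at the last visit reached, up to W.

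**Why 52-82.** Counting back from 01 September 2017, Week 52 means randomisation by 2 September 2016 and Week 82 by 5 February 2016. Week 88 needs 25 December 2015, and Weeks 94 and 96 need 13 November and 30 October 2015. The protocol is dated 22 October 2015 and screening takes at least 7 days (Protocol 6.2.1). Even spread up to Weeks 94-96 would therefore need full-rate randomisation within one to three weeks of the protocol date.

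**Week 76 in full.**

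- Withdrawal: (0.750 + 0.698 + 0.650 + 0.604 + 0.5625)/5 = 0.653, against a true 0.5625.
- Continued: (0.900 + 0.877 + 0.854 + 0.832 + 0.810)/5 = 0.854, against a true 0.810.

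Percentages below are true / LOCF / error, with errors taken from unrounded values. The error is an overstatement in each arm and an understatement of the difference.

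| Visit | Reached | Withdrawal | Continued | Difference |
|---|---|---|---|---|
| Week 64 | 60% | 65.0 / 67.9 / 3.0 | 85.4 / 86.8 / 1.4 | 20.4 / 18.8 / 1.6 |
| Week 70 | 40% | 60.4 / 66.1 / 5.7 | 83.2 / 85.9 / 2.7 | 22.7 / 19.7 / 3.0 |
| Week 76 | 20% | 56.3 / 65.3 / 9.0 | 81.0 / 85.4 / 4.4 | 24.8 / 20.2 / 4.6 |

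**Sensitivity at Week 76.**

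- Half the hazard after Week 52: withdrawal 69.9 vs 65.0 (4.9), continued 87.7 vs 85.4 (2.3), difference understated by 2.6.
- Both arms lose at the continued arm's rate after Week 52: withdrawal 71.2 vs 67.5 (3.7), continued 4.4, so the difference is overstated by 0.7.
- No further loss: 0.

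At Week 52 the error is 0 in every case, because every subject still in the trial has reached that visit.

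**Scale.** The approximate 95% half-width for the Week 76 difference at the LOCF rates is 1.96·√(0.653·0.347/204 + 0.854·0.146/102) = 9.5 points.

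**The case against.** **No confirmatory result is affected.** This stands. Protocol 7.4 notes that "All primary and key secondary endpoints are collected by Week 52". The SAP adds a Week 104 ranked endpoint but tests it in the final analysis only (10.3.1.2), and that analysis will replace these displays. The Part B primary is at Week 52, where NRI is the primary approach.

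**The error does not favour the drug in the comparison.** A reader might infer that carrying responses forward inflates the advantage of staying on treatment. The documents do not support that. Under the plan's own pattern of faster loss off drug, the difference is understated. It is overstated only if later loss is about equal in the two arms, and then slightly (0.7 points above).

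**The size rests on extrapolation.** This also stands. The 25% and 10% apply at Week 52 only. Permanent loss is not the plan's rule: relapse needs sPGA of 3 or more, so a subject at sPGA 2 stays on blinded treatment and may regain 0 or 1. Recovery would flatten the net decline and reduce the bias. A lock later than the last patient's Week 52 raises minimum follow-up and also reduces it at a given visit.

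**Retreated subjects are not the source.** Under LOCF they carry their last value before retreatment, normally an sPGA of 3 or more, so they remain sPGA non-responders. The excess comes from responders whose later visits are not yet due.

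None of this removes the fault: the rule reports rates for visits that most subjects may not have reached, without saying so.

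**Conclusion.** The concern holds as a minor-to-moderate improvement to secondary, provisional displays. The direction is conditional. Both arms are overstated only if response is still being lost after Week 52; the withdrawal arm is overstated more, and the difference understated, only if loss is also faster off drug. The Weeks 64-76 errors in the table are illustrative and depend on the assumed follow-up and loss.

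Two stronger readings are tempting. One is an error above 10 points at Week 88. That needs subjects randomised by 25 December 2015 in appreciable numbers, which fits poorly with the stated dates unless the efficacy cutoff is later, and a later cutoff also lengthens minimum follow-up. The other is that the confidence intervals are shown to be falsely narrow. Comparing the LOCF interval with a Kaplan-Meier one is like for like only if loss is permanent, which the plan does not state.

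**What to change.** Choose one of two changes to SAP 10.1:

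- Delete the exception, so that visit-wise response stops at Week 52 at this lock.
- Keep it, but state an efficacy cutoff and limit each visit after Week 52 to subjects whose visit was due by then on the original schedule (Table 8 target days). Keep relapsed and retreated subjects in the denominator, and show the numbers due and observed at each visit.

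If durability past Week 52 is wanted at this lock, the Kaplan-Meier time-to-loss and time-to-relapse analyses in 10.1.3 can be run to the same cutoff. The Week 52 limit in 10.1 covers them too, so it must be amended. It would also help to state in 10.1.3 that subjects still on study are censored at their last measurement.

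The cost is less, or less precise, information past Week 52 at this lock. With restricted denominators the cohort also changes from visit to visit. There is no confirmatory cost.

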10.1.2 Analyses of Continuous Variables

For continuous variables, the model based mean and standard error will be presented. The Baseline and visit means will also be presented for each treatment group for subjects who have both Baseline and post Baseline visit values. The treatment groups will be compared using ANCOVA with treatment group, Baseline value, and stratification factors in the model.

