4.2 Design Diagram

This is a confirmatory, multinational, multicenter, randomized, double-blind, placebo controlled study with randomized withdrawal and retreatment, evaluating the safety and efficacy of risankizumab 150 mg subcutaneous (SC) in patients with moderate to severe chronic plaque psoriasis.

The study consists of an up to 42 day screening period, a 16-week double-blind, placebo-controlled initial treatment period (Part A1), a 12-week treatment period (Part A2), an up to 60-week continuous treatment and treatment withdrawal period (Part B) with possible retreatment with risankizumab for up to 16 weeks, and a 16 week follow-up period.

Part A1: A 16-week double-blinded, placebo-controlled treatment period during which subjects will be randomized at a ratio of 4:1 to one of two treatment arms as shown in [Figure 1](#). Arm 1 refers to those subjects originally randomized to risankizumab and Arm 2 refers to those subjects originally randomized to placebo. The first dose of study drug will be administered on Day 1 (Visit 2; Baseline) and the second dose will be administered at Week 4. The randomization will be stratified with respect to weight (≤ 100 kg vs. > 100 kg) and prior exposure to TNF antagonists (0 vs. ≥ 1).

[figure not shown]
Part A2: A 12-week treatment period. At Week 16, all subjects will receive one dose of risankizumab 150 mg.

Part B: At Week 28, non-responders (static Physician Global Assessment [sPGA] ≥ 2) will receive open label risankizumab 150 mg every 12 weeks with a last dose at Week 88 (end-of-treatment, EOT), while responders (sPGA of 0 or 1) from Arm 1 will be

re-randomized in a 1:2 ratio to either maintain risankizumab 150 mg or matching placebo every 12 weeks with a last dose at Week 88 (EOT). The re-randomization will be stratified with respect to weight (≤ 100 kg vs. > 100 kg) and prior exposure to TNF antagonists (0 vs. ≥ 1). Responders from Arm 2 will continue to receive blinded risankizumab 150 mg every 12 weeks with a last dose at Week 88 (EOT) to maintain the blind. Throughout the SAP, "re-randomized" or "re-randomization" refers to the randomization at Week 28 among subjects from Arm 1 of Part A.

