4.3 Sample Size

This study is designed to show a difference between risankizumab and placebo in terms of achieving 90% reduction in Psoriasis Area and Severity Index (PASI 90) response and sPGA of clear or almost clear (sPGA of 0 or 1) at Week 16. This study was also powered to show a difference in sPGA response at Week 52 between the subjects re-randomized to continue on risankizumab vs. subjects randomized to placebo at Week 28.

Based on the interim results from Study 1311.2, it is assumed at most 10% of the subjects in the re-randomized risankizumab arm and approximately 25% of subjects in the re-randomized placebo arm will lose response. Using a 1:2 re-randomization scheme (risankizumab:placebo), 102 subjects in the risankizumab arm and 204 subjects in the

placebo arm will provide at least 90% power to detect the difference in sPGA response rate at Week 52. Assuming that 80% of subjects initially randomized to risankizumab at baseline will achieve sPGA of 0 or 1 at Week 28, the total sample size required for the initial risankizumab arm at Visit 2 is $(102)(3) \div 0.8 = 383$.

A total sample size of 500 = 400:100 for risankizumab: placebo was planned at Visit 2.

Based on the outcome from Trials 1311.1 and 1311.2, the PASI 90 response rate at Week 16 is assumed to be at least 65% in the risankizumab arm and approximately 5% for placebo. For sPGA clear or almost clear at Week 16, the response rate is assumed to be at least 80% for the risankizumab arm and approximately 5% for placebo. This trial will have > 99% power for comparing risankizumab arm to placebo on both of these endpoints.

All calculations were performed using ADDPLAN Version 6.0.4, an Aptiv Solutions Company.

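### The common-variance ANCOVA misstates the standard error for PASI change: too small in Part A (4:1), slightly too large in Part B (1:2)

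*SAP*

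**What the plan says.** SAP 10.1.2 sets the output for continuous endpoints: "For continuous variables, the model based mean and standard error will be presented". The comparison follows in the same section: "The treatment groups will be compared using ANCOVA with treatment group, Baseline value, and stratification factors in the model". It mentions no unequal-variance model, robust covariance or treatment-by-baseline term, and it names no confidence interval.

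SAP 10.1 fixes the test level ("The treatment effect will be evaluated based on a two-sided significance level of 0.05") and where comparisons are made ("The efficacy analysis will be conducted in the ITT_A1 and the ITT_B_R populations"). Neither population has equal arms. For Part A, "A total sample size of 500 = 400:100 for risankizumab: placebo was planned at Visit 2". For Part B, Protocol 7.7 plans that "102 patients in the BI 655066 arm and 204 patients in the placebo arm will provide at least 90% power".

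Continuous endpoints appear only among the further efficacy endpoints (SAP 10.3.3). The co-primary, Part B primary, ranked and other secondary endpoints are all binary. They use the stratified risk difference of SAP 10.1.1, whose variance has a separate term for each arm.

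**The concern.** An ordinary ANCOVA estimates one residual variance over both arms. With equal arms, unequal spread does little harm to the SE of the difference. With unequal arms, the pooled variance is dominated by the larger arm. The SE is too small when the smaller arm is the more variable one, and too large when the larger arm is.

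The planning assumptions point to unequal spread for PASI. SAP 4.3 says the "PASI 90 response rate at Week 16 is assumed to be at least 65% in the risankizumab arm and approximately 5% for placebo". Most risankizumab patients would then sit close to a score of zero, while placebo patients keep most of their baseline spread. For absolute change the single slope adds to this. On active drug, change is close to minus the baseline score; on placebo it is not. A slope set mainly by 400 active patients pushes baseline spread into the placebo residuals.

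In Part A the variable arm is the small one. In Part B the withdrawn arm, expected to be the more variable, is the large one. At stake are the SEs and p-values published for PASI change and percent change at every visit, and any later use of those SEs.

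**Working it through.** **1. The plan's own figure.** Neither document gives an SD, SE or sample size for a continuous endpoint. The stated Part B size can be checked. With 90% against 75%, ratio k = 2, two-sided 0.05, 90% power, pooled variance and no continuity correction, the weighted mean rate is (0.90 + 2 × 0.75)/3 = 0.80, and

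n = [1.96·√(0.80·0.20·1.5) + 1.2816·√(0.90·0.10 + 0.75·0.25/2)]² / 0.15² = (0.960 + 0.549)² / 0.0225 ≈ 101.3, so 102 against 204.

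Then 306/0.8 = 382.5, so 383. The plan's figures reproduce.

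**2. Effect of pooling.** Let r be the placebo residual SD divided by the risankizumab residual SD, which is set to 1. With n₁ on risankizumab and n₀ on placebo,

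SE ratio = √{ s_p²(1/n₁ + 1/n₀) / (1/n₁ + r²/n₀) }, where s_p² = [(n₁−1) + (n₀−1)r²]/(n₁+n₀−2), and coverage = 2Φ(1.96 × SE ratio) − 1.

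Example, Part A, r = 2: s_p² = (399 + 99·4)/498 = 1.596. The SE ratio is √(1.596 × 0.0125 / 0.0425) = 0.685, and coverage is 82.1%.

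| r (assumed) | Part A 400:100, model SE / true SE | Coverage | Part B 102:204, model SE / true SE | Coverage |
|---|---|---|---|---|
| 0.67 | 1.26 | 98.7% | 0.88 | 91.5% |
| 1 | 1.00 | 95.0% | 1.00 | 95.0% |
| 1.25 | 0.88 | 91.4% | 1.08 | 96.5% |
| 1.5 | 0.79 | 87.9% | 1.14 | 97.4% |
| 2 | 0.69 | 82.1% | 1.23 | 98.4% |
| 3 | 0.59 | 75.4% | 1.32 | 99.0% |

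**3. What r the planning rates suggest for PASI, Part A.** Inputs: 65% against 5% PASI 90 (SAP 4.3) and 87% PASI 75 on active drug in phase I (Protocol 1.2). Assumption: the remaining fraction of baseline PASI follows a beta distribution. The active fit has mean 0.104 and SD 0.131. For placebo, fixing 5% PASI 90 and assuming a mean remaining fraction of 0.6 to 0.9 gives an SD of 0.258 to 0.300. So r is about 2.0 to 2.3, the SE ratio 0.69 to 0.65, and coverage 82% to 80%.

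**4. The same for Part B.** Inputs: 10% against 25% losing response (Protocol 7.7). SAP 10.1.4 carries the value before retreatment forward, so relapsed patients keep a raised score. Assumption: a mixture in which those who keep response have a remaining fraction with mean 0.03 and SD 0.04, and those who lose it have mean μ and SD s. The variance is (1−p)·0.04² + p·s² + p(1−p)(μ−0.03)². With μ = 0.4 and s = 0.15 it is 0.0325 at p = 0.25 and 0.0160 at p = 0.10, so r = √2.03 = 1.42. With μ from 0.3 to 0.5 (s = 0.15, or 0.2 at μ = 0.5), r runs from 1.41 to 1.44 and the SE is about 12% too large.

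**5. Simulation of the SAP's ANCOVA** (treatment, baseline, two strata; 4,000 trials per row). Assumptions: baseline PASI = 12 + gamma with mean 8; strata prevalences 30% and 35%; placebo mean remaining fraction 0.8 in Part A; μ = 0.4 in Part B.

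| Comparison | Mean model SE | Mean HC3 SE | Empirical SD | Model coverage | HC3 coverage |
|---|---|---|---|---|---|
| Part A, change | 0.490 | 0.792 | 0.782 | 77.5% | 95.0% |
| Part A, percent change | 1.972 | 3.037 | 3.033 | 79.4% | 94.5% |
| Part B, change | 0.421 | 0.380 | 0.375 | 96.9% | 95.1% |
| Part B, percent change | 1.960 | 1.760 | 1.788 | 97.0% | 95.0% |

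Model SE over empirical SD is 0.63 and 0.65 in Part A, and 1.12 and 1.10 in Part B.

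**6. Sensitivity to shape.** Further simulations let placebo patients without PASI 90 keep a mean of 85% to 90% of baseline, with SD 10% to 40% of baseline. Model SE over true SE stayed within about 0.58 to 0.80, with coverage 75% to 88%. Even the narrowest placebo spread (SD 10%) gave only 85.5% for change and 87% for percent change. At 10% against 25% in Part B, the SE excess over all shapes tried was 7% to 15%, with coverage about 96% to 97%.

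**The case against.** The strongest reply is that nothing confirmatory depends on this. That stands: every continuous endpoint is unranked, and the binary analyses already use arm-specific variance. For PASI in Part A the decision is also safe. In simulation the test statistic is about 27 to 34 in absolute value with the model SE and still 15 to 21 with HC3. In Part B at 10% against 25% it is about 2.6 against 2.9. Protocol 7.3.3 also plans SDs and IQRs for these endpoints, so unequal spread would be visible if those summaries are produced.

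Three stronger readings are tempting and are not supported.

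- **All continuous endpoints are affected.** A reader might infer this because the model applies to all of them. No figure in either document bears on the relative spread of DLQI, NAPSI, PPASI, PSSI, the VAS scales, HAQ-DI or DAS28. With equal spread there is no error, and with r below 1 both directions reverse.
- **Part B wastes about 40% of its information.** That needs an SE about 30% too large (1 − 1/1.30² = 41%). At the planned loss rates the excess is 7% to 15%, or 13% to 24% of the information (1 − 1/1.07² to 1 − 1/1.15²). The planned 10% is an upper bound. At 5% against 25% or 60%, one set of simulations gave about 20% to 22%; 5% against 50% gave 26% to 27% in another. Losses of 50% or 60% appear nowhere in the plan. No calculation shows that a withdrawal effect on any weaker endpoint would be hidden.
- **The plan specifies faulty confidence intervals.** SAP 10.1.2 names an SE and a comparison only. Coverage is used here to express the size of the SE error, which the p-value shares.

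**Conclusion.** The concern holds for change and percent change in PASI. In Part A the stated analysis would report an SE about 0.6 to 0.8 of the true one, so the SE and p-value overstate precision (nominal 95% coverage about 75% to 88%). In Part B at the planned rates the SE is about 7% to 15% too large, a modest and conservative error.

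The direction for PASI follows from the plan's response rates under every shape tried. The size rests on assumed distributions (beta and mixture shapes, placebo mean and spread, baseline PASI), because neither document gives an SD. For the other continuous endpoints neither presence nor direction can be derived.

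No primary, ranked or other secondary conclusion changes. The reason to act is that the published precision for PASI change would be wrong, and the correction costs almost nothing.

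**What to change.** Add one sentence to SAP 10.1.2: the ANCOVA point estimate is kept, and its SE, p-value and any confidence interval come from an HC3 heteroscedasticity-consistent covariance matrix, in both ITT_A1 and ITT_B_R. A residual variance estimated separately by arm is an acceptable alternative, optionally with a treatment-by-baseline term.

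The cost is that sentence and one software option. Design and sample size do not change. Part A SEs for PASI become larger, as they should, and Part B SEs become slightly smaller. If the variances prove equal, almost nothing changes.

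One limit: HC3 was checked only for PASI at full arm sizes, where coverage was about 93% to 96%. The joint counts, DAS28, HAQ-DI and VAS endpoints are restricted to confirmed psoriatic arthritis patients, assessed at selected sites only. That subset has no stated size, and HC3 should be checked there before it is relied on.
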